7.1. General Methods

- Unless otherwise specified, summaries will be presented by study period, by treatment group and overall.
- Continuous variables will be summarized using the number of observations (n), mean, standard deviation (SD), standard error of mean, median, first and third quartiles, minimum and maximum. Categorical variables will be summarized using number of observations (n) and percentages (%) of patients. The 95% CI around the mean may also be presented in descriptive statistics as appropriate for specific endpoints of interest.
- All relevant patient data will be included in listings. All patients entered into the database will be included in patient data listings

7.2. Key Definitions

7.2.1. First Dose Date

First dose date is defined as the day of first dose of study treatment received after randomization.

7.2.2. Last Dose Date

Last dose date is defined as day of the last dose of study treatment.

For patients ongoing for the treatment period at time of analysis prior to database lock, the last dose date is the date of the most recent study visit where study drug was administered in the database for the patient.

7.2.3. Study Day

The study day is determined relative to the date of first dose of study treatment, unless otherwise specified. The day of the first dose of study treatment is defined as study day 1. The day prior to the first dose of study treatment is study day -1. There is no study day 0.

For events that occur before the first dose of study treatment,

study day = date of the event – first dose date;

for events that occur on or after the first dose of study treatment,

study day = date of the event – first dose date + 1.

7.2.4. Baseline and Change from Baseline

For all change from baseline variables, the baseline is defined as the last non-missing assessment prior to or on the day of randomization, and must be prior to the first administration of study treatment, including scheduled and unscheduled visits, unless otherwise specified. Hence, change from baseline = post-baseline value – baseline value.

The baseline value for analyses of qualitative parameters (e.g., normal/abnormal) is defined as the last evaluation prior to or on the day of randomization, and must be prior to the first administration of study treatment.

This document is confidential.

The baseline value for the PRO questionnaires and diary will be the average of the 7 days before starting study treatment.

7.3. Missing Data

Missing data imputation rules for efficacy data are specified in Section エラー! 参照元が見つかりません。 All other missing data not covered here will not be imputed. Analyses will be performed considering all data observed for the respective analysis sets.

7.3.1. Partial or Missing Event Dates

All partial or missing dates will be presented in the data listings as they are recorded on the electronic Case Report Form (eCRF). The analysis dataset will flag where day, month or year has been imputed for analysis start or stop date.

7.3.2. Adverse Events

For the purpose of assessing whether an AE is treatment emergent, if an AE has a completely missing start and stop date, it will be considered treatment emergent; if the stop date is not missing, but the start date is completely missing, it will be considered treatment emergent unless the stop date occurs prior to the first dose of study drug.

For purpose of calculation of duration of AE, if a completely missing start and stop date occurs then it will be considered to have started on the date of first dose and stopped at the date of study termination. If stop date is present, and start date is completely missing, the start date will be imputed with the date of first dose of study drug unless the stop date occurs prior to first dose of study drug; in this case the start date will be imputed with the date of first dose of study drug. If start date is present and a completely missing stop date occurs, it will be considered to have stopped at the date of study termination for the patient.

For assessing treatment emergence or for calculation of duration of AE, if a partial start or stop date occurs, the following imputation process will be implemented:

Partial Missing Start or Stop Date	Imputation for Start Date	Imputation for Stop Date
Day missing, month and year present	
Month and/or year different to month and year of first study drug dose: Impute day with "01".Month and/or year same as month and year of first study drug dose: Impute day with same day as first dose of study drug.	Impute day with last day of the month
Day and month missing, year present	
Year different to year of first study drug dose: Impute day and month with "01JAN".Year same as year of first study drug dose: Impute month and day with same month and day as first dose of study drug.	Impute day and month with "31DEC"
Month missing, day and year present	
Year different to year of first study drug dose: Impute month with "JAN".Year same as year of first study drug dose: Impute month with same month as first dose of study drug.	Impute with "DEC"
Caveats	
If any imputed start date leads to a start date that is after the stop date, then the start date will be imputed with the date of the stop of AE.	

This document is confidential.

If the start date of any TEAE is incomplete or missing, the event will be assumed to be in the Induction Period, unless the incomplete start date (month and/or year) clearly indicates that the event started on or after the first dosing in Maintenance Period.

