4.1.3. Maintenance Period (week 16 to week 52)

The patients who received placebo during the Induction Period will receive loading doses of lebrikizumab at Weeks 16 and 18. To maintain blinding at Weeks 16 and 18, all patients will receive 2 injections at Weeks 16 and 18 (either 2 injections of lebrikizumab or 1 injection of lebrikizumab and 1 injection of placebo). From Week 20 onward, all patients will receive open label 1 injection of lebrikizumab 250 mg every 2 weeks (Q2W).

4.1.4. Extension Period for Germany according to Protocol Amendment 4

According to Local protocol amendment 4 for Germany (dated 2-Feb-2023), Extension Period treatment duration is a minimum of 6 months (24 weeks) following Week 52 and until lebrikizumab is commercially available in Germany. Maintenance dose changed to once every 4 weeks (Q4W) during the Extension Period, with return to once every 2 weeks (Q2W) allowed at the Investigator's discretion.

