7.3.3. Prior/Concomitant Medications

For the purpose of assessing whether a medication is prior or concomitant, if a medication has a completely missing start date it will be considered a prior medication, and if a medication has a completely missing stop date it will be considered a concomitant medication. If a partial start or stop date occurs, the following imputation process will be implemented:

Partial Missing Start or Stop Date	Imputation for Start Date	Imputation for Stop Date
Day missing, month and year present	
Month and/or year different to month and year of first study drug dose: Impute day with "01"Month and/or year same as month and year of first study drug dose: Impute day with same day as first dose of study drug.	Impute day with last day of the month
Day and month missing, year present	
Year different to year of first study drug dose: Impute day and month with "01JAN"Year same as year of first study drug dose: Impute month and day with same month and day as first dose of study drug.	Impute day and month with "31DEC"
Month missing, day and year present	
Year different to year of first study drug dose: Impute month with "JAN"Year same as year of first study drug dose: Impute month with same month as first dose of study drug.	Impute with "DEC"
Caveats	
If any imputed start date leads to a start date that is after the stop date, then the start date will be imputed with the date of the stop of medication.No stop date will be imputed if the treatment is ongoing.	

If the start date of any medication/procedure is incomplete or missing, and it is unclear when imputed whether the medication/procedure started in Induction or Maintenance Period, the medication/procedure will be assumed to be concomitant with both Induction and Maintenance Period, unless the incomplete start date (month and/or year) clearly indicates that the medication/procedure started on or after the first dosing in Maintenance Period.

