9.7. Maintenance Period (and Extension Period for Patients from Germany) Analyses

The Induction and Maintenance/Extension Periods will be reported separately. For the Maintenance/Extension Period, the same analyses as for Induction Period, as described in section エラ
ー! 参照元が見つかりません。, will be performed descriptively on the FAS.

This document is confidential.

10. Safety

The population used for safety analyses will be the Safety Analysis Set (SAF). Safety will be assessed based on adverse event (AE), treatment emergent adverse event (TEAE), vital signs, laboratory results, and physical examinations.

Safety will be described by treatment groups:

- Up to Week 16: Lebri / Placebo
- Up to Week 52/68/Extension period: Lebri-Lebri / Placebo-Lebri

All safety analysis except for laboratory evaluations/vital signs/physical examinations will be summarized for the three study periods described below:

- Induction Period (up to Week 16),
- Maintenance Period and Safety Follow-up:
 - For all patients: from Week 16 to Week 52
 - For all patients except German patients in the extension: from Week 16 to 68
 - For German patients in the extension: from Week 16 to last visit in the German extension
- Combined Induction and Maintenance/Extension Periods (up to Week 52 or later for the Extension as described above – see maintenance period), and Combined Induction and Maintenance/Extension Periods plus Follow-Up Period [selective analysis] (Up to Week 68 or later for the Extension as described above – see maintenance period).

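### Adverse events with unclear start dates default to the Induction Period, so some that began on lebrikizumab after the Week 16 switch can be tabulated under placebo and lost from the Maintenance tables

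*SAP*

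**What the plan says.** The rule for placing an adverse event in a study period closes SAP Section 7.3.2: "If the start date of any TEAE is incomplete or missing, the event will be assumed to be in the Induction Period". The one exception is a partial date whose known month or year makes plain that onset was no earlier than the first Maintenance dose. The rule covers any treatment-emergent event in either arm and looks only at the partial start date. An event with no dates at all reaches this rule, because the same section states that "if an AE has a completely missing start and stop date, it will be considered treatment emergent".

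Two other parts of the SAP give the rule its effect:

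- Section 4.1.3: "The patients who received placebo during the Induction Period will receive loading doses of lebrikizumab at Weeks 16 and 18". From then on these patients stay on lebrikizumab.
- Section 10 sets the safety treatment labels. The first reads "Up to Week 16: Lebri / Placebo". After that point the groups are relabelled by sequence, as Lebri-Lebri and Placebo-Lebri.

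For medications, Section 7.3.3 handles an unclear start differently: "the medication/procedure will be assumed to be concomitant with both Induction and Maintenance Period", subject to the same kind of exception for a partial date that is clear.

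**The concern.** In a placebo-randomised patient, the Week 16 injection is the boundary between no exposure to lebrikizumab and first exposure. A default to Induction resolves doubt towards the unexposed period. If the event in fact began after the switch, two things follow. It appears under placebo in the Induction tables, which are the only placebo-controlled safety comparison. It is also absent from the Maintenance tables, where these patients are newly starting the drug. The adverse events of special interest, conjunctivitis and herpes infection, are summarised by the same study periods. For uncommon events of that kind one or two patients could be visible in a table.

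Section 7.3.2 uses the stop date to decide whether an event is treatment emergent, but not to decide which period it belongs to. The SAP plans no sensitivity analysis for events placed by default.

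**Working it through.** The documents give no figure for this point, so there is nothing to reproduce. The arithmetic below is illustrative. It assumes a constant onset rate, full follow-up and first doses spread evenly over the calendar.

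**Inputs**
- Induction is 16 weeks and treatment lasts to Week 52 (SAP 4.1).
- Adverse events are collected to 18 weeks after the last dose, which is Week 68 for a completer (Protocol 10.6.3 and 7.1).
- Planned arms are 208 lebrikizumab and 104 placebo (SAP 4.3).

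**Step 1. Wholly missing start date.** Every such event goes to Induction. The share whose true onset is after Week 16 is:
- to Week 52: (52 − 16)/52 = 36/52 = 69%
- to Week 68: (68 − 16)/68 = 52/68 = 76%

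**Step 2. Partial start date, among events that truly began after Week 16.** Let T be the length of follow-up after Week 16: 36 × 7 = 252 days to Week 52, or 52 × 7 = 364 days to Week 68.
- *Only the year known.* The exception fails when onset falls in the calendar year of the switch. With the switch date uniform over a 365-day year, the share sent to Induction is 1 − T/(2 × 365). This gives 1 − 252/730 = 65% and 1 − 364/730 = 50%.
- *Only the day missing.* The exception fails when onset falls in the calendar month of the switch. On average about 15 days of that month remain, so the share is about 15/252 = 6% or 15/364 = 4%.

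A simulation under the same assumptions gave 65% and 50% for year-only dates, and 6% and 4% for day-missing dates.

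**Step 3. Effect of one patient.** A misplaced event changes an incidence only if the patient had no such event in Induction already. It then adds 1/104 = 0.96 points in the placebo arm, or 1/208 = 0.48 points in the lebrikizumab arm.

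**Step 4. Effect on the Induction comparison.** Let the rule add proportion a_P to placebo and a_L to lebrikizumab. The risk difference moves by a_L − a_P, whose sign the rule does not determine. Suppose a_L = a_P = a, with assumed true rates of 9% on lebrikizumab and 3% on placebo (risk ratio 3.0, difference 6 points):

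| a | Risk difference | Risk ratio |
|---|---|---|
| 0 | 6 points | 9/3 = 3.0 |
| 1 point | 6 points | 10/4 = 2.5 |
| 2 points | 6 points | 11/5 = 2.2 |
| 3 points | 6 points | 12/6 = 2.0 |

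With the rates reversed, one added point moves the ratio from 3/9 = 0.33 to 4/10 = 0.40. The pull is towards 1 in both cases, so it helps lebrikizumab where its rate is higher and hurts it where its rate is lower.

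**Step 5. Effect on the Maintenance tables.** Any event moved to Induction is removed from Maintenance. In both groups that event arose on lebrikizumab, so these tables can only lose on-drug events.

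**The case against.** The strongest objection concerns direction. A reader might infer that the rule favours lebrikizumab throughout, by raising the placebo rate in Induction and lowering the rate on drug afterwards. The first half is not supported. Section 7.3.2 applies to both arms, and the lebrikizumab arm has twice as many patients whose late events can be moved forward. Similar added percentages leave the risk difference about where it was. The second half, fewer on-drug events in the Maintenance tables, does stand.

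A reader might also infer that the imputation of day 01 in the Section 7.3.2 table produces the same misplacement. It does not. That table serves treatment emergence and duration, and Section 10.1 says that only emergence is imputed and that dates are not. The period rule alone creates the problem. The two sections should still be reconciled, since one imputes dates and the other says it will not.

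The parallel with medications is imperfect. Section 8.6.2 assigns a medication to the periods in which it is ongoing, so one medication can belong to two periods, whereas an event is placed by its onset. Section 7.3.3 therefore serves as a workable precedent for unclear records; it does not show that the SAP contradicts itself.

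The number affected should be low. Adverse events are asked about at every scheduled visit, mostly two weeks apart, start and end dates are to be recorded (Protocol 10.6.2), and data are queried and cleaned (Protocol 12.2). Events of special interest are reported within 48 hours, with a dedicated form for conjunctivitis (Protocol 10.6.1). The exception disposes of most day-missing dates. The combined-period tables and the listings still contain every event. All of this limits the size; none of it corrects the attribution in the period tables.

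**Conclusion.** The point holds in a limited form. The stated rule can attribute to placebo an event that began on lebrikizumab, and can remove on-drug events from the Maintenance tables. In the Induction comparison it dilutes the risk ratio towards 1 without a determined shift in the risk difference. The documents therefore do not support a claim that the controlled comparison is tilted in favour of lebrikizumab.

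The size is unknown because the share of events with incomplete start dates is not given, and it is probably small. Exposure lies mainly in wholly missing dates, of which 69% to 76% would truly fall after Week 16, and year-only dates, of which 50% to 65% of true later onsets would be misplaced. Day-missing dates contribute about 4% to 6% of true later onsets. These percentages rest on the constant-rate and full-follow-up assumptions above. The primary efficacy analysis is not affected.

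**What to change.** Amend the period rule in SAP Section 7.3.2, identically for both arms:

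1. Keep the exception for a partial start date that clearly shows onset at or after the first Maintenance dose. Equally, assign to Induction alone an event whose partial start date clearly precedes that dose.
2. Otherwise use the stop date where it settles the matter: a stop date before the Week 16 injection means Induction.
3. Count an event that remains unresolved in both periods, as Section 7.3.3 does for medications, and once only in combined-period tables.
4. Report the number of unresolved events by arm, with a sensitivity table that assigns them all to Maintenance.

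Do not set different defaults by arm. Sending only the placebo-arm events to Maintenance would leave late events in the Induction count for lebrikizumab alone and would bias the randomised comparison against it.

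While amending, reconcile Section 7.3.2 with Section 10.1 on whether event dates are imputed.

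The cost is a few sentences and one table, best settled before unblinding so that the choice is not made after the results are seen. The downside is that a few events appear in both period tables and may be over-attributed to lebrikizumab. The main Induction table also still contains the unresolved events, which is why the sensitivity table is needed.

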7.3.3. Prior/Concomitant Medications

For the purpose of assessing whether a medication is prior or concomitant, if a medication has a completely missing start date it will be considered a prior medication, and if a medication has a completely missing stop date it will be considered a concomitant medication. If a partial start or stop date occurs, the following imputation process will be implemented:

Partial Missing Start or Stop Date	Imputation for Start Date	Imputation for Stop Date
Day missing, month and year present	
Month and/or year different to month and year of first study drug dose: Impute day with "01"Month and/or year same as month and year of first study drug dose: Impute day with same day as first dose of study drug.	Impute day with last day of the month
Day and month missing, year present	
Year different to year of first study drug dose: Impute day and month with "01JAN"Year same as year of first study drug dose: Impute month and day with same month and day as first dose of study drug.	Impute day and month with "31DEC"
Month missing, day and year present	
Year different to year of first study drug dose: Impute month with "JAN"Year same as year of first study drug dose: Impute month with same month as first dose of study drug.	Impute with "DEC"
Caveats	
If any imputed start date leads to a start date that is after the stop date, then the start date will be imputed with the date of the stop of medication.No stop date will be imputed if the treatment is ongoing.	

If the start date of any medication/procedure is incomplete or missing, and it is unclear when imputed whether the medication/procedure started in Induction or Maintenance Period, the medication/procedure will be assumed to be concomitant with both Induction and Maintenance Period, unless the incomplete start date (month and/or year) clearly indicates that the medication/procedure started on or after the first dosing in Maintenance Period.

7.4. Visit Windows

In general, all data from the eCRF will be organized and analyzed according to the scheduled time points. If the scheduled assessment is available, any additional or unscheduled assessments will not be used in the summary statistics per time point (unless otherwise discussed in the relevant section), but will be included in the data listings according to the date/time of assessment.

If the scheduled assessment is not available, the unscheduled assessment will be used if it is collected within from -6 to +7 days of the target day/timepoint for the scheduled assessment. If there are some unscheduled assessments available, the closest data to the Day will be used. If there are prior and post-Day data within same days from the Day, the later post-Day data will be used.

The unscheduled assessment could be available based on the following visit windows.

This document is confidential.

Scheduled assessment Visit - Week	Lower allowance	Target day	Upper allowance
Visit 3 - Week 2	8	14	21
Visit 4 - Week 4	22	28	35
Visit 5 - Week 6	36	42	49
Visit 6 - Week 8	50	56	63
Visit 7 - Week 10	64	70	77
Visit 8 - Week 12	78	84	91
Visit 9 - Week 14	92	98	105

7.5. Adjustments for Covariates

Unless otherwise specified, the statistical analysis models for the Induction Period efficacy and health outcome analysis will include the following stratification factors for Baseline randomization: age (adolescent patients 12 to <18 versus adults ≥18 years) and baseline disease severity (IGA=3 versus IGA=4). Additionally, the following factors will be included in the models:

- Country of patient as recorded at screening
- For analyses of the full population (i.e. not the subgroups of dupilumab naïve or previously exposed patients), the stratification factor of prior use of dupilumab (yes/no) will be included.

If the model does not converge, country will be removed as a factor from the specific model.

7.6. Subgroups

All endpoints will be analysed by previous exposure to dupilumab (Yes/No) as CCI .

For the maintenance phase, the analysis will be performed for both arms separately:

- Lebrikizumab (patients previously took lebrikizumab)
- Lebrikizumab (patients previously took placebo)

7.7. General Considerations for Efficacy during Induction Period

The Induction Period starts after the first injection of study treatment at Baseline Visit (Day 1) and ends prior to the first injection of study treatment at Week 16 or the early termination visit (ETV) (between Day 1 and Week 16). For patients who are randomized but not dosed, the Induction Period starts on the date of randomization.

For Pruritus Numeric Rating Scale (NRS) and Sleep-Loss due to Pruritus collected via eDiary, the baseline period is the 7-day window prior to the first injection. A patient must have responses on at least 4 of 7 days to calculate a baseline weekly mean. If a patient has 3 or fewer responses, the baseline mean value will be considered missing.

